Faculty of Nursing

Obstetrics & Gynecologic Nursing Department

Protocol for postdoctoral research

In Obstetric & Gynecologic Nursing

Academic Year 2020-2021

Title:

In English:

Effect Of Trendelenburg Position, Warm Pad Application and Deep Breathing Exercise on Shoulder Pain and Post Gynecologic Laparoscopic Recovery

Keywords: Trendelenburg position, Warm Pad, Breathing exercise, Gynecologic laparoscopy, shoulder pain, postoperative recovery.

INTRODUCTION

Laparoscopic gynecologic surgery has evolved from a limited surgical procedure used only for diagnostic purposes to a major surgical approach for treating a multitude of malignant and non-malignant pathologies. It is currently considered one of the most common surgical procedures performed by gynecologists.(**Zeein et al., 2020**) . Laparoscopic surgery, has become widely recognized as a viable alternative to traditional laparotomy in treatment of different gynecologic diseases (**Hsuan et al., 2019**). The advantages of laparoscopic surgery over traditional laparotomy include a smaller surgical wound, less postoperative pain, a shorter hospital stay, faster recovery, and a better cosmetic result. (**chen et al., 2011**). However, post-laparoscopic shoulder pain (PLSP), is a prevalent complaint following laparoscopic surgery with an incidence as high as 80%. The pain can be severe and is usually relieved in 24–48h, but rarely persists for over 72h after surgery. It has also been found that PLSP is less responsive to treatment than incision and visceral pain (**Kiyak, 2019**).

The precise mechanism of post-laparoscopic shoulder pain remains unclear. Carbon dioxide accumulation and phrenic nerve irritation as a result of diaphragmatic stretching are the most accepted explanations(**Phelps, 2008**). A number of techniques that are proposed to diminish shoulder pain as intraperitoneal instillation of local anesthetics, pulmonary recruitment maneuver, warm and humidified dioxide, low pressure pneumoperitoneum and intraperitoneal normal saline infusion. Unfortunately, these interventions have often found quite varied and sometimes even conflicting results regarding their effectiveness (**Tian, 2021**).

Optimal pain management is imperative for the success of immediate and long term rehabilitation. Therefore, relieving PLSP is a problem that can no longer be ignored. Effective pain control is best achieved through a combination of both pharmaceutical and non-pharmaceutical therapies. Non pharmacological methods increase women/Patient control of her feeling, improve the activity level and functional capacity and reduce dosage of analgesic drugs thus decreasing the side effects of treatment (**Metawie et al.,2015**).

One of the popular non-pharmacological techniques is heat therapy, it is easy to use, inexpensive, require no prior practice, and have minimal side effects when used properly. In addition to being used for pain relief, heat is used to relieve chills or trembling, decrease joint stiffness, reduce muscle spasm, and increase connective tissue extensibility (**Mohamed & Elhady, 2016**).

Also, one of the recommended non-pharmacological actions is to use deep breathing relaxation techniques. The technique of breathing relaxation itself is an act of nursing care, which in this case the nurse teaches the patients how to do deep breathing techniques, slow breathing (hold inspiration to the maximum) and how to exhale slowly. In addition to reducing pain intensity, deep breathing relaxation techniques can also improve lung ventilation and increase blood oxygenation (**Asman & Maifita, 2019**).

In addition, the trendelenburg position might decrease shoulder pain by reducing the mechanical pressure exerted by CO₂ on the diaphragm and the upper abdominal muscles. CO₂, known for its high solubility, would also be displaced to the pelvis that has a rich vasculature which in turn speeds up the resorption of pneumoperitoneum (**Zeein et al., 2020**). However, evidence-based research is still needed in the area of pain relief after gynecologic laparoscopy and few studies have attempted to identify the effect of warm application and trendelenburg position versus deep breathing technique on PLSP. So, the purpose of this study is to determine the effect of postoperative trendelenburg position, warm application, and deep breathing exercise on shoulder pain

AIM OF THE STUDY

The present study aims to:

investigate the effect of postoperative trendelenburg position versus warm pad application and deep breathing technique on shoulder pain intensity and post gynaecologic laparoscopic recovery

Hypothesis

- Women who assume trendelenburg position after gynecological laparoscopic surgery exhibit less shoulder pain intensity and high quality postoperative recovery than those who receive warm application and who perform deep breathing technique.
- Women who receive warm pad application after gynecological laparoscopic surgery exhibit less shoulder pain intensity and high-quality postoperative recovery than those who assume trendelenburg position and who perform deep breathing technique.
- Women who perform deep breathing technique after gynecological laparoscopic surgery exhibit less shoulder pain intensity and high-quality postoperative recovery than those who assume trendelenburg position and who receive warm application.

PLAN OF THE STUDY

MATERIALS AND METHOD

Materials

Research design:

A comparative quasi-experimental research design will be utilized in this study, where the effect of three independent variables (Trendelenburg position, heating pad and deep breathing technique on two dependent variables (shoulder pain and post gynecologic laparoscopic recovery) will be examined in this study.

Setting:

This study will be conducted in the laparoscopic unit at El Shatby Maternity University Hospital in Alexandria Governorate, Egypt. This hospital was particularly chosen because the turnover of gynecologic laparoscopy is suitable for the study and the women attending this hospital have nearly the same socio-economic status which maintain homogeneity of the study sample

Subjects:

A convenient sample of 90 women attending the previously mentioned setting will be recruited. The Epi info 7 program version 10 was used to estimate the sample size using the following parameters; Population size= (1000) over 3months, Expected frequency 50%, Acceptable error of 5%, and Confidence coefficient 95%. The minimum sample size 84

women will be selected according to the following criteria:

- Age from 18-70 years
- who were scheduled for diagnostic or operative gynecological laparoscopic surgery for non-malignant pathologies (e.g., hysterectomy, myomectomy, ovarian

cystectomy)

- Free from any medical or gynecological risk factors such as, morbid obesity (BMI > 45). Medical history of deep vein thrombosis, rupture of ectopic pregnancy, rupture of an ovarian cyst, shoulder surgery and chronic shoulder pain.

Sampling technique: The selected subjects were assigned to one of the following two groups:

- Study group 1 included 30 women, who will assume the trendelenburg position.
- Study group 2 involved 30 women, who will receive the warm pad on shoulder
- Study group 3 included 30 women who will perform deep breathing technique

Tools:

Three tools will be developed and used by researcher to collect the necessary data as following:

Tool (I): woman's Socio-demographic and Clinical Data Structured Interview Schedule

This tool will be developed by the researcher. It entails the following two sections:

Part (I): Socio-demographic characteristics such as: the subjects' age, level of education and occupation. In addition to her marital status, residence, family type and income etc.-----.

Part (II): Profile of current gynecologic surgery including: name, date, duration, reason for surgery and postoperative complaint.

Tool (II): Postoperative Quality of Recovery scale(QoR40)

This tool was originally developed by Myles (2000), (Myles et al., 2000) it is used to measure quality of recovery. It is consisted of 40 items, the items are grouped according to various aspects (dimensions) of recovery: emotional state (9items), physical comfort (12items), psychological support (7items), physical independence (5 items), and pain (7items). Subjects' response to each item will vary according to a 5 point likert scale, it was scored for positive item as "1= none of the time, 2=some of the time, 3= usually,4=most of time, and 5=all of the time. For negative items the scoring will be reversed.

Total score of QoR scale will range from (40- 200) scores, the total quality of recovery score was calculated as the following:-

Low quality of recovery-----< 60% of total quality of recovery scores (< 120 scores).
Moderate quality of recovery -----60-75% of total quality of recovery scores (< 120-150 scores). High quality of recovery ----->75% of total quality of recovery scores (> 150-scores).

Tool (III): Numerical Pain Rating Scale (NRS)

This tool will be adapted from the Clinical Manual for Nursing Practice (McCaffery, M. and Beebe, A. ,1993) (McCaffery& Beebe.,1993). It will be used to assess the severity of shoulder pain. Women will be instructed to choose a number from 0 to 10 that best describes their current pain. 0 means "No pain" and 10 means sever pain'. It was scored as no pain (0), mild pain (1-3), moderate (4-7), and sever pain (8-10).

METHOD

The study will be accomplished according to the following steps:

1. An official approval will be obtained from the Research Ethics Committee, Faculty of Nursing, Alexandria University. An official letters from the Faculty of Nursing, Alexandria University will be directed to the responsible authorities of the study settings to obtain the permission to collect data after explaining the study purpose.
2. Tool (I) will be developed by the researcher after thorough review of recent& relevant literature.
3. Tool (II, III) will be adapted and translate into Arabic language to suite Egypt culture.
4. Tools will be tested for content validity by a jury of 5 experts in Obstetrics and Mental health fields.
5. Tools will be tested for their reliability by using the appropriate test.
6. A pilot study will be carried out on 9 women; to test the feasibility of the study as well as to ascertain the clarity and applicability of the tools in addition to calculate the time needed to complete them. (This number will be excluded from the study).

7. Each woman in the two groups will be individually interviewed during the preoperative period to collect basic data using tool I.
8. Again, for women undergoing the present study, the researchers will reassure that they have the same technique of surgery, doses of anesthetic drugs, and intra-operative measures to drain CO₂ gas from the abdominal wall .
9. The subjects will be assigned to one of 3 groups as follows:
 - **Group 1** (trendlenburg position group) in which the women will be positioned in a Trendelenburg position (20 °) once fully awake and cooperative in the recovery room and will remain in this posture for the first 24 hrs postoperatively. The maximum time allowed in a straight-up position will be three 15-min intervals over a 24-h period.
 - **Group 2** (warm pad application group) in this group warm pad (38°C -40°C) will be applied on the shoulder after four hours postoperatively for a period of 5-10 minutes. Each woman will be asked to place heat pads when needed during the first 24 hours.
 - **Group 3:** (deep breathing group) the researcher will instruct women after the end of surgery and upon consciousness to take slowly deep breathing while observing her chest and hold her breath for about 5 seconds and then exhale slowly, repeating this deep breathing technique five times after full vigilance within the first 3 hours after surgery. Then, the process will be repeated 6, 12, and 24 h later. The patient will be instructed about this type of breathing before surgery by researchers.
10. Pain intensity will be evaluated for all groups 4 times: at arrival to recovery room, & 4, 6, 12 and 24 hours postoperatively using tool III.
11. postoperative recovery will be evaluated for all groups after 24 h postoperatively using tool II
12. Comparison between all groups will be done to determine which intervention induces less shoulder pain and improve in postoperative recovery.

Ethical considerations:

For each recruited subject the following issues will be considered:

- Written informed consent will be obtained from women before data collection after explanation of the study aim.
- Privacy of women will be maintained during data collection processes.
- Confidentiality of data will be maintained during the execution of the study.
- Women's anonymity will be maintained during the execution of the study.
- Women will be informed that their participation in the study is voluntary, and they can withdraw at any time.

RESULTS

Analysis of data will be carried out by the researcher with the help of a statistical specialist. The collected data will be categorized, coded, computerized, tabulated and analyzed, using SPSS program.

DISCUSSION

The obtained findings will be explained and compared to current related literature and recent researches in the field.

CONCLUSION AND RECOMMENDATIONS

Conclusion and recommendations will be derived from the findings of the study.

REFERENCES

- Asman, A., & Maifita, Y. (2019). Effect of Deep Breathing Relaxation Techniques for Reducing Pain after Hernia Surgery in Inpatient of Regional Hospital Pariaman West. *Age (years)*, 50(64), 65.

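### The stated sample-size inputs give 278 women, not 84, and they size a one-proportion survey, so the three-group comparison of 90 women has no valid sample-size basis

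*Protocol*

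**What the plan says.** The sample size is justified in the Subjects section under Materials and Method. It opens with "A convenient sample of 90 women attending the previously mentioned setting will be recruited". It continues with "The Epi info 7 program version 10 was used to estimate the sample size using the following parameters", and the inputs and result follow: "Population size= (1000) over 3months, Expected frequency 50%, Acceptable error of 5%, and Confidence coefficient 95%. The minimum sample size 84".

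Under Sampling technique the 90 women are divided into three groups of 30 (Trendelenburg position, warm pad, deep breathing). The Tools section defines the two outcomes: shoulder pain on a 0–10 numerical scale, and QoR-40 recovery on a scale from 40 to 200. Method, step 12, gives the purpose of the data: "Comparison between all groups will be done to determine which intervention induces less shoulder pain and improve in postoperative recovery". Each of the three hypotheses claims that one intervention is better than the other two.

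The protocol has no other sample-size statement.

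**The concern.** There are two separate problems.

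First, the result does not follow from the inputs printed beside it. Population size, expected frequency, acceptable error and confidence level fully determine the answer, and that answer is far from 84.

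Second, even a correct answer would address a different question. Those four inputs fix how precisely one percentage is estimated in one population. They say nothing about the chance of detecting a difference between groups, which is what all three hypotheses and step 12 require.

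An ethics committee or a reader would take a minimum of 84 with 90 recruited to mean that the comparison is adequately sized with a small margin. The protocol does not support that reading. All three groups receive an active intervention, so a non-significant result could easily be reported as showing that the interventions are equally good. With 30 per group that conclusion may well not be justified.

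**Working it through.** **Inputs, all from the Subjects section:** N = 1000, p = 0.50, d = 0.05, and 95% confidence (z = 1.96). Stated result: 84. Planned: 90 women, 30 per group (Sampling technique).

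**1. Reproducing the stated figure.** For one proportion with finite-population correction:

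n = N·p(1−p) / [(d²/z²)(N−1) + p(1−p)]

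- Numerator: 1000 × 0.25 = 250.
- Denominator: (0.0025/3.8416) × 999 + 0.25 = 0.6501 + 0.25 = 0.9001.
- n = 250/0.9001 = 277.7, rounded up to **278**.

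Ratios: 278/84 = 3.3 and 278/90 = 3.1.

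**2. Looking for a variant that gives 84.**

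| Variant | n |
|---|---|
| No finite-population correction | 385 |
| N/(1 + N·d²) | 286 |
| 90% confidence (or one-sided 95%) | 214 |
| Expected frequency 80% | 198 |
| Population of one month (333) | 179 |
| 80% confidence | 142 |
| Error 10% in place of 5% | 88 |

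None gives 84. The closest, 88, needs twice the stated error and still differs. To reach 84 with the other inputs unchanged, the error would have to be about 10.2% (84.6 at d = 0.102), or the population about 107 (83.9 at N = 107, 84.5 at N = 108). Each contradicts a stated input.

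**3. Precision at the planned size.** Half-width = z·√[(p(1−p)/n)·(N−n)/(N−1)], with N = 1000 and p = 0.50:

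- n = 84: 1.96 × √[(0.25/84)(916/999)] = ±10.2 points.
- n = 90: 1.96 × √[(0.25/90)(910/999)] = ±9.9 points.
- n = 30 (one group): ±17.6 points (±17.9 without the correction).

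The stated error is ±5 points.

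**4. What 30 per group can detect.** The protocol gives no difference, SD or power, so no required sample size for the comparison can be computed from it. The reverse question can be answered in SD units. For a two-sample t-test at one time point, two-sided, 80% power:

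- α = 0.05: 0.736, so about **0.74 SD**.
- α = 0.05/3 (Bonferroni over three pairs): 0.857, so about **0.86 SD**.

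The normal approximation, (z₁₋α/₂ + z₀.₈₀)·√(2/30), gives slightly smaller values: 0.72 and 0.84. For a difference of 0.5 SD, t-test power is about 48% (31% at 0.05/3).

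The SD of the pain score is not given. If it is assumed to be 2.0 to 2.5 points, 0.74 SD is 1.5 to 1.8 points and 0.86 SD is 1.7 to 2.1 points.

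**The case against.** The arithmetic is not in dispute, but four objections deserve an answer.

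- **Which number is the slip is unknown.** The text shows only that inputs and result disagree. If the population of 1000 is the error and the true figure is about 107, then 84 and ±5% are consistent as a survey calculation. This stands as a caveat: the half-widths above are conditional on the protocol's own 1000. It does not rescue the justification, because a consistent survey calculation would still not size a comparison.
- **The detectable differences are illustrative.** The protocol names no two-sample t-test. Pain is measured repeatedly, including on arrival in the recovery room, so a baseline-adjusted or repeated-measures analysis might detect smaller differences. Bonferroni is one choice; with exactly three groups, an omnibus test followed by unadjusted pairs also controls the family-wise error. This stands: 0.74 and 0.86 SD describe one simple analysis, and the 0.86 SD one multiplicity rule.
- **Nothing shows that 90 is too few.** True. Thirty per group could suffice if large differences are expected. The point is that the protocol neither states nor justifies such an expectation.
- **278 is not a shortfall.** Also true. It answers a question the trial does not ask, and the factor of 3.3 measures the arithmetic error, not missing women.

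An unseen statistical analysis plan would not settle the matter, because the protocol itself states the inputs and a result that does not follow from them.

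**Conclusion.** The concern holds, and the paragraph must be corrected. The stated inputs give 278, not 84, and no conventional variant tried gives 84. This rests only on figures in the protocol. The method is also of the wrong type for a comparison of three groups on two scores, so neither the minimum of 84 nor the planned 90 has a valid basis in the document. Wrong method is the more serious half, since correcting 84 to 278 would not repair it.

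On a simple pairwise t-test at two-sided 5%, 30 per group gives 80% power for 0.74 SD, or 0.86 SD under Bonferroni, which are large differences. Conversion to pain-scale points depends on an assumed SD. Whether 90 women are enough cannot be decided from the protocol.

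**What to change.** Delete the single-proportion calculation and the figure of 84. Keep 90 women, 30 per group, and justify the size by what it can detect, for example: *With 30 women per group, a two-sided 5% pairwise comparison has 80% power for a difference of 0.74 SD (0.86 SD after Bonferroni adjustment for three comparisons).*

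Add the pain-score SD that the sponsor assumes, with its source, so that the difference can be read in scale points, and name the outcome and time point to which the statement applies. If another multiplicity rule or a baseline-adjusted analysis is planned, recompute the figure for that analysis. Say explicitly that smaller differences cannot be excluded and that a non-significant result will not be taken as evidence that the interventions are equivalent.

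The cost is one rewritten paragraph. The change itself requires no extra women and leaves treatment and assessments as they are. The protocol loses its claim to exceed a computed minimum and states a more modest aim in its place.

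### Step 8 promises uniform surgery and anesthesia while eligibility runs from diagnostic laparoscopy to hysterectomy, and no stated assignment rule keeps procedure type comparable across the three groups

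*Protocol*

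**What the plan says.** **Uniformity.** Method, step 8, commits the researchers to ensuring that "they have the same technique of surgery, doses of anesthetic drugs, and intra-operative measures" for draining CO2 from the abdomen apply to the women in the study.

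**Eligibility.** The criteria under Subjects take women "scheduled for diagnostic or operative gynecological laparoscopic surgery for non-malignant pathologies (e.g., hysterectomy, myomectomy, ovarian" cystectomy). The list is introduced as examples, so other benign procedures also qualify.

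**Design and assignment.** Under Research design: "A comparative quasi-experimental research design will be utilized in this study". Under Subjects: "A convenient sample of 90 women attending the previously mentioned setting will be recruited". Method, step 9, says only: "The subjects will be assigned to one of 3 groups as follows". Each group has 30 women. No random sequence, stratification or matching is mentioned.

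**Data on the operation.** Tool I, Part II, records the "name, date, duration, reason for surgery and postoperative complaint". Nothing in the protocol links these items to assignment.

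**Use of the comparison.** Step 12 compares all groups to decide which intervention gives less shoulder pain and better recovery.

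**The concern.** Step 8 is where the protocol deals with differences in surgery and anesthesia, and it does so by declaring them the same. Taken with the eligibility list, that is hard to sustain: a diagnostic laparoscopy and a hysterectomy are different operations and can be expected to differ in length. If the operation is not in fact constant, comparability has to come from how women are assigned, and the protocol gives no rule for that.

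The protocol's own introduction makes this relevant. It names CO2 accumulation and phrenic nerve irritation from diaphragmatic stretching as the most accepted explanations of the pain. Type and length of operation could plausibly act through either, and could also affect recovery at 24 hours. A group that happens to receive more of the shorter cases could then look better in step 12 for a reason unrelated to its intervention, or a real difference between interventions could be hidden.

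**Working it through.** The protocol gives no figure on this point, so there is none to reproduce. The check is mainly a reading of the passages side by side.

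**1. Can step 8 and eligibility both hold as written?**

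| Element in step 8 | What the rest of the protocol adds |
|---|---|
| Same surgical technique | Not defined; eligible procedures run from diagnostic laparoscopy to hysterectomy |
| Same anesthetic doses | No account of how this would hold across those procedures |
| Same CO2-drainage measures | Compatible with mixed procedures |
| Procedure type and duration | Not named in step 8; both can vary |
| A woman whose surgery differs | Nothing is said about what happens to her |

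The third row is consistent. The first two cannot be squared with the eligibility list until the protocol says what is meant. The fourth row is left open on any reading.

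**2. Does assignment balance what step 8 leaves open?** Women are recruited by convenience and assigned to groups by an unstated rule. Systematic differences in procedure type and duration between groups are therefore not ruled out. The homogeneity argument under Setting is socio-economic, not surgical.

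**3. How large could the effect be?** The protocol gives no case mix, no standard deviation and no effect of procedure on pain. The following is an illustration only, and every input except the 30 per group is an assumption.

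- Bias = (systematic difference in the share of major procedures) x (NRS difference between major and minor procedures).
- Share difference 0.2, that is 6 of 30 women: 0.2 x 1 = 0.2 points; 0.2 x 2 = 0.4 points.
- Share difference 0.3, that is 9 of 30 women: 0.3 x 2 = 0.6 points.

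Effect on one pairwise test at two-sided 5%, with SE = SD x sqrt(2/30) and false-positive rate = Phi(b/SE - 1.96) + Phi(-b/SE - 1.96), where b is the bias:

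| SD (assumed) | SE | b = 0.2 | b = 0.4 | b = 0.6 |
|---|---|---|---|---|
| 1.5 | 0.39 | 8.1% | 17.8% | 34.1% |
| 2.0 | 0.52 | 6.7% | 12.1% | 21.3% |
| 2.5 | 0.65 | 6.1% | 9.5% | 15.3% |

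For example, with SD 2 and b = 0.4: b/SE = 0.4/0.516 = 0.775, and Phi(-1.185) + Phi(-2.735) = 0.118 + 0.003 = 0.121.

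These rates describe a difference in case mix that the assignment process itself produces. They do not say that such a difference will occur.

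**The case against.** **Step 8 is a commitment, not a description.** It can be read as a further condition on the eligible pool, and technique may mean only a common laparoscopic method with a common gas-release routine. That is fair, and on this reading there is no strict contradiction about technique. It does not explain identical anesthetic doses, and it does not balance procedure type or duration between groups.

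**Other restrictions limit case mix.** Surgery is for non-malignant pathology, and ruptured ectopic pregnancy, ruptured ovarian cyst, shoulder surgery, chronic shoulder pain and BMI above 45 are excluded. This stands: step 8 is not the only safeguard. But these criteria narrow the pool as a whole; they do not equalise the groups.

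**The link from procedure to shoulder pain is inferred.** The introduction calls the mechanism unclear and never says that duration or procedure type alters the pain. This stands too, and is why the bias is described as possible.

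**Mixed procedures are a legitimate choice, and the root problem is assignment.** Agreed. Under randomisation, mixed procedures would mainly add variance. Case mix is one concrete route by which unspecified assignment can do harm.

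**Adjustment belongs in an SAP.** Agreed. The SAP is not at hand, so the absence of covariates or by-group tables is not counted against the protocol.

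**A stronger reading to avoid.** A reader might work out how often groups of this size differ by 20 percentage points or more in their share of diagnostic cases. With independent binomial draws in three groups of 30, some two groups do so with probability 0.27 if 30% of women are diagnostic cases and 0.33 if 50% are (both shares assumed). It would be wrong to offer this as the size of the bias. It is chance imbalance under random assignment, which a valid test already allows for and which any unstratified randomised trial of this size would share.

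**Conclusion.** The point holds as a need to reconcile two passages and as a weakness in assignment. Step 8 does not say what is constant across operations as different as those the eligibility list admits, and no stated rule keeps procedure type and duration comparable between groups. The step 12 comparison of shoulder pain and QoR-40 is therefore open to confounding by the operation.

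The documents do not show that such confounding will occur, and its size cannot be calculated from them. The shifts of 0.2 to 0.6 NRS points, and the matching false-positive rates of about 6% to 34%, depend wholly on the assumed case-mix differences, procedure effects and standard deviations. At the lower end the distortion is small on a 0 to 10 scale. The change is worth making because it is cheap and removes a systematic route to a wrong ranking of the three interventions.

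**What to change.** 1. Reconcile step 8 with the eligibility list: state which elements of surgery, anesthesia and gas drainage are held constant, which may vary, and how a woman who does not fit is handled in the study. Which surgical or anesthetic rule applies is for the investigators to settle.
2. Assign women by a random sequence stratified by planned procedure class as known before surgery, for example diagnostic, minor operative and major operative. A simple split into diagnostic and operative would put cystectomy and hysterectomy together. The design description should be revised to match.
3. Unless the SAP already does so, adjust the NRS and QoR-40 comparisons for procedure class and duration of surgery. This is a secondary aid. Duration cannot be a stratification factor because it is known only after the operation, but Tool I, Part II, already captures it.

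**Cost.** Revised wording, a stratified set of assignment lists where the protocol now describes none, and a slightly larger model. Group sizes may end slightly off 30 if a stratum closes part-way through a block. No extra women and no extra data are needed.

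### QoR-40 has no preoperative measurement in a non-randomised comparison, so baseline differences in its domains can bias the 24-hour recovery contrast and can be neither shown nor adjusted for

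*Protocol*

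**What the plan says.** Under Research design, the Protocol names shoulder pain and postoperative recovery as its two dependent variables and states: "A comparative quasi-experimental research design will be utilized in this study". On sampling, Subjects states: "A convenient sample of 90 women attending the previously mentioned setting will be recruited". Sampling technique and Method step 9 divide the women 30:30:30. Step 9 says only "The subjects will be assigned to one of 3 groups as follows" and gives no mechanism for the assignment.

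Tool II is the QoR-40, with a total from 40 to 200. Its five dimensions are emotional state, comfort, psychological support, independence and pain. Step 11 gives its only administration: "postoperative recovery will be evaluated for all groups after 24 h postoperatively using tool II". Before surgery, each woman is "individually interviewed during the preoperative period to collect basic data using tool I". Tool I covers socio-demographic characteristics and a profile of the operation.

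Step 12 sets the comparison: "Comparison between all groups will be done to determine which intervention induces less shoulder pain and improve in postoperative recovery". The first hypothesis is also a contrast between groups, namely that women in the Trendelenburg position "exhibit less shoulder pain intensity and high quality postoperative recovery than those who receive warm application and who perform deep breathing technique". The other two hypotheses have the same form.

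**The concern.** All five QoR-40 dimensions describe states that a woman already has before her operation. Eligibility is wide: ages 18 to 70, and diagnostic as well as operative laparoscopy, from ovarian cystectomy to hysterectomy. Chronic shoulder pain is an exclusion, but other preoperative pain and low mood are not listed.

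Without described randomisation, nothing in the design makes these states equal on average across the three groups. If one group starts with poorer mood or comfort, its intervention can look worse at 24 hours for that reason alone. Because no preoperative QoR-40 is collected, the report could neither show such a difference nor adjust for it. The trial also gives up the precision that a baseline covariate may bring, with only 30 women per group.

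This is not a matter that an analysis plan can settle later. An analysis plan can adjust only for data that have been collected, and the Protocol fixes the assessment schedule.

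**Working it through.** **1. What is measured before treatment**

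| Item | Where | Baseline for QoR-40? |
|---|---|---|
| Tool I: demographics, profile of the operation | Tools; step 7 | Indirect at best |
| Same surgical technique, anaesthetic doses and CO₂ drainage | Step 8 | Controls the operation, not the woman's preoperative state |
| Pain rating on arrival in the recovery room | Step 10 | No: taken after surgery, shoulder pain only |
| Tool II (QoR-40) | Step 11 | Given only at 24 hours |

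**2. Inputs for size**

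The Protocol gives n = 30 per group. It gives no QoR-40 standard deviation, expected difference or correlation between preoperative and 24-hour scores. Its sample-size statement rests on a single proportion, so it supplies none of these. There is thus no figure in the plan to reproduce on this point, and everything below except n is an assumed range.

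**3. Precision**

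Adjusting for a baseline with correlation r leaves residual variance 1 − r². The equivalent increase in sample size is 1/(1 − r²).

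- r = 0.3: 1 − 0.09 = 0.91, a fall of 9%; 1/0.91 = 1.10
- r = 0.5: 1 − 0.25 = 0.75, a fall of 25%; 1/0.75 = 1.33
- r = 0.6: 1 − 0.36 = 0.64, a fall of 36%; 1/0.64 = 1.56

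This is like having 10 to 56% more women per group.

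**4. Bias in points**

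Bias = slope × preoperative difference. With an assumed slope of 0.5 and an assumed difference of 10 points, 0.5 × 10 = 5 points at 24 hours with no treatment effect.

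**5. Bias in standard deviations (SD) and its effect on a pairwise test**

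Take equal SDs at both times, so that the slope equals r, and widen the range of r to 0.7. The standard error of a difference between two groups is √(2/30) = 0.258 SD. For bias b = r × imbalance, the two-sided 5% error rate becomes Φ(−1.96 + b/0.258) + Φ(−1.96 − b/0.258).

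| r | Imbalance (SD) | Bias (SD) | False-positive rate |
|---|---|---|---|
| 0.3 | 0.25 | 0.075 | 6.0% |
| 0.3 | 0.50 | 0.150 | 8.9% |
| 0.5 | 0.25 | 0.125 | 7.7% |
| 0.5 | 0.50 | 0.250 | 16.2% |
| 0.7 | 0.25 | 0.175 | 10.4% |
| 0.7 | 0.50 | 0.350 | 27.3% |

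These rates apply to a systematic imbalance of the stated size. For scale, 0.25 SD is about one standard error (0.25/0.258 = 0.97).

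**6. Detectable difference at 80% power, one pairwise test**

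(1.960 + 0.842) × 0.258 × √(1 − r²) gives 0.72 SD without a baseline, and 0.69, 0.63 and 0.52 SD at r = 0.3, 0.5 and 0.7.

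**The case against.** A reader might infer from the word improve in step 12 that the recovery question cannot be answered at all without a baseline. The documents do not support that. Step 12 opens by announcing a comparison between groups, all three hypotheses are between-group contrasts, and Tool II is read against absolute bands (below 120, 120 to 150, above 150). No change-from-baseline endpoint is defined. One 24-hour score per woman is enough to compute the contrast, and improve is loose wording.

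A reader might also infer that any preoperative difference carries over in full. That is too strong as well. With a slope of 0.5, half of it does. The Protocol also offers partial control: the exclusion criteria, a site chosen for similar socio-economic status, the uniform technique in step 8, and Tool I variables that can be compared and adjusted for.

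Two further objections stand. The root weakness is the unstated, non-random assignment. With sound randomisation the systematic bias would go and mainly the precision argument would remain. And no size given here rests on a QoR-40 figure from the Protocol. The tool is described there as a postoperative measure, still to be translated and tested, so how well a preoperative score predicts the 24-hour score is unknown.

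None of this disposes of the narrower point. Tool I is at best a proxy for preoperative mood, comfort and pain, and step 8 standardises the procedure, not the women.

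**Conclusion.** The point holds as a limited design weakness that is cheap to mend. It is not an error that invalidates the recovery comparison. In a non-randomised design, preoperative differences in the QoR-40 domains can bias the 24-hour contrast, and the planned data can neither show them nor adjust for them directly. The contrast remains computable; only within-woman improvement cannot be shown.

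The size is conditional. A 10-point preoperative difference becomes 5 points if the slope is 0.5, and residual variance falls by 9 to 36% if r lies between 0.3 and 0.6. For imbalances of 0.25 to 0.5 SD and r from 0.3 to 0.7, the pairwise false-positive rate would be about 6 to 27% instead of 5%. Nothing in the Protocol shows that imbalances of that size will occur; equally, nothing planned would reveal them. The priority is low, but the gap must be closed before recruitment, because a preoperative score cannot be recovered after surgery.

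**What to change.** - Step 7: give Tool II once at the preoperative interview, preferably before the woman knows her group and before any breathing instruction.
- Report the preoperative QoR-40 total by group.
- Step 12: compare the 24-hour total between groups by analysis of covariance, with the preoperative total as covariate, and word the aim as a higher 24-hour recovery score.
- Step 6: use the pilot in 9 women to check that the items can be answered before surgery and how long they take.

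The cost is one 40-item questionnaire per woman at an interview already planned, plus one covariate; no extra visit or procedure is needed. Adjustment would reduce confounding by preoperative state. It would not remove confounding by unmeasured factors, so the assignment method in step 9 still has to be stated and dealt with in its own right.
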